**Adenoma Detection Rate With a New Pediatric Colonoscope With a Short Turn Radius
(Pentax Retroview) Compared With a Standard Pentax Pediatric Colonoscope**

Date of Document: 6/13/2014

Adenoma detection rate with a new pediatric colonoscope with a short turn radius (Pentax Retroview) compared with a standard Pentax pediatric colonoscope.

[name]
Principal Investigator

I. BACKGROUND AND SIGNIFICANCE

Colonoscopy is widely thought to be the best screening test for detection of colorectal polyps and cancers. However, colonoscopy is not a perfect test and 6-11% of large polyps and higher numbers of smaller polyps may be missed during routine colonoscopy. The colon is a tube like organ but has many folds, and some polyps may be located proximal to (behind) these folds. One of the reasons polyps may be missed at colonoscopy is that a standard colonoscope cannot easily look behind colonic folds. The purpose of the study is to evaluate whether a new colonoscope that can easily bend to look behind these folds can detect more polyps than a standard colonoscope. As colorectal cancer is the second most common cause of cancer related mortality in the United States with over 50,000 deaths reported annually, the impact of such new knowledge would be highly significant. One of the reasons for the development of these interval colon cancers is polyps missed at colonoscopy. Polyps that are located on the proximal side of haustral folds or flexures can be difficult to detect using a conventional forward-viewing colonoscope and may contribute to adenoma miss rates. It is plausible to hypothesize that the inability to efficiently look behind colonic folds may therefore contribute to the development of interval colon cancers. An improved colonoscope that finds more precancerous and cancerous lesions could potentially protect more patients from colon cancer and decrease interval cancer rates.

Colorectal Cancer in the United States

Of cancers that affect both men and women, colorectal cancer is the second leading cause of cancer death in the United States. In 2006, 139,000 patients were newly diagnosed with colorectal cancer, and 53,000 patients died from it. Colorectal cancer is thought to develop from precancerous polyps.

Colorectal Cancer Screening, Adenoma Miss Rates and Interval Cancers

The current standard of care to prevent colorectal cancer includes colonoscopy with removal of adenomatous polyps of the colon and rectum. There is evidence that screening with colonoscopy and removal of polyps decreases the incidence of colorectal cancer compared to reference populations that are not screened. Though colonoscopy is an important method to detect precancerous polyps, it is not perfect. Tandem colonoscopy studies (where patients undergo two colonoscopies, the second performed immediately following the first) indicate a >20% miss rate for adenomatous polyps at the first colonoscopy, even when the procedure is performed by skilled endoscopists. It is known that in patients who have a normal colonoscopy, a small number will develop 'interval' colorectal cancer prior to the next planned surveillance colonoscopy. In one study of patients with colorectal cancer, 5% had a reportedly normal colonoscopy in the three years prior to diagnosis.

One of the reasons for the development of these interval colon cancers is polyps missed at colonoscopy. Polyps that are located on the proximal side of haustral folds or flexures

can be difficult to detect using a conventional forward-viewing colonoscope and may contribute to adenoma miss rates. It is plausible to hypothesize that the inability to efficiently look behind colonic folds may therefore contribute to the development of interval colon cancers.

Colonoscopes that Offer a Retrograde View:

Recently, devices that allow visualization behind haustral folds with a retrograde view have been developed with the objective to discover lesions missed by conventional endoscopy. One such device is the Third Eye Retroscope, a retrograde viewing device that is advanced through the accessory channel of the endoscope. This device provides a simultaneous anterograde and retrograde view of the colon as the colonoscope is withdrawn. In a multi-center study utilizing this device 448 patients underwent two colonoscopies, once with the colonoscope plus the Third Eye and once by standard colonoscopy. The order was randomized. The second look by Third Eye colonoscope found more additional adenomas (46% more) than a second look by standard colonoscope (20% more). This suggests that the benefit of the Third Eye Retroscope exceeds the benefit of a second look endoscopy by a standard colonoscope.

Performance and Retroflexion Properties of Colonoscopes

In contrast to a retrograde viewing device that is passed through the colonoscope's accessory device, another option for allowing a retrograde view is a colonoscope whose tip is able to bend with a shorter turning radius than a traditional colonoscope. Current colonoscopes have a longer bending radius at the tip of the instrument which makes bending the tip backwards (retroflexion) to visualize the proximal aspect of colonic folds difficult.

Kessler et al. showed that a prototype pediatric colonoscope with a short bending section at the tip was able to successfully retroflex at the cecum more often compared to one with a standard bending section, without compromising the ability to reach the cecum or need to change patient position.

We plan to study a new pediatric colonoscope (Pentax Retroview) which has a short turning radius and can easily retroflex within the colon to provide both an anterograde and retrograde view, though not simultaneously. Pediatric colonoscopes are widely used for adult colonoscopy, and are more flexible than adult colonoscopes. We have studied the new colonoscope in anatomic bench models, and it led to higher detection rates of simulated polyps, especially those found behind folds. This study will compare the detection of precancerous and cancerous lesions utilizing the new colonoscope to that of a standard pediatric colonoscope with a standard bending section. We will measure the number of precancerous and cancerous lesions found at the colonoscopy.

References

Colorectal (Colon) Cancer. Centers for Disease Control and Prevention. 6 Jul 2010.



Waye JD, Heigh, JH et al. A retrograde viewing device improves detection of adenoma in the colon: a prospective efficacy evaluation (with videos). *Gastrointestinal Endoscopy*. 2010 Mar; 71(3):551-6.

II. SPECIFIC AIMS

Objective: We would like to learn whether the new colonoscope that provides both a traditional and a retrograde view (bending 180 degrees to look behind itself) of the colon can detect more polyps than a standard colonoscope that only provides a forward-facing view. We wish to effectively demonstrate the utility of the new colonoscope (Pentax Retroview Colonoscope) as the objective of this study is to determine polyp (adenoma) detection rates in human subjects undergoing colonoscopy for polyp surveillance.

III. SUBJECT SELECTION

Subjects will be recruited from patients already referred to the physician investigators for surveillance due to personal history of colon polyps found during colonoscopy done 3 or more years previously. This will allow for evaluation of the colonoscope in a population that requires surveillance colonoscopy. The physician investigators have a sufficiently large referral base for surveillance colonoscopy that will allow recruitment for this number of participants. The participants will be undergoing a colonoscopy by attending endoscopists, regardless of whether they enroll in the study or not.

This is a multi-site study.

IV. SUBJECT ENROLLMENT

For those randomized to the new colonoscope, the colonoscope will provide a forward-facing view of the colon during advancement to the cecum (standard of care). The scope will then be withdrawn all the way to the rectum and the colon will be inspected using the forward-facing view (standard of care). The colonoscope will then be re advanced to the cecum and be withdrawn using the retrograde view.

For those randomized to the control arm, colonoscopy will be performed with a conventional colonoscope. During withdrawal in the control group, the colon will be inspected using the forward-facing view (standard of care). The colonoscope will then be re-advanced to the cecum and again withdrawn using the forward-facing view.

Patients will be randomized equally to either the new colonoscope (Pentax Retroview) or the control arm with a standard pediatric colonoscope. A total of 300 subjects will be enrolled.

V. STUDY PROCEDURES

1. Patients with prior history of colon polyps (adenomas) are referred for surveillance colonoscopy (standard of care) due to personal history of colon polyps found during colonoscopy done 3 or more years previously
2. The patients will undergo standard bowel preparation for colonoscopy (standard of care)
3. Patients will be asked during routine pre-procedure examination for colonoscopy if they are interested in participating in the study
3. Following consent, patients will be randomized to colonoscopy with either the new colonoscope or conventional colonoscope.
4. Patients will undergo colonoscopy (standard of care). All colonoscopies will be performed by a GI attending.

For those randomized to the new colonoscope, the colonoscope will provide a forward-facing view of the colon during advancement to the cecum (standard of care). The scope will then be withdrawn all the way to the rectum and the colon will be inspected using the forward-facing view (standard of care). The colonoscope will then be re advanced to the cecum and be withdrawn using the retrograde view. In subjects that are randomized to the Retroview scope, the scope is advanced to cecum and then withdrawn to rectum in forward position. The subject is reintubated. At the cecum, scope is retroflexed and withdrawn till before hepatic flexure. Then straightened out, pulled through flexure and retroflexed again. The scope is withdrawn through transverse in retroflexed view until the rectum. There has been a 50 subject trial in which the withdrawal time was recorded and an additional 9.8 minutes were added to the total withdrawal time. It is unknown if there is additional risk in the retroflexed view.

For those randomized to the control arm, colonoscopy will be performed with a conventional colonoscope. During withdrawal in the control group, the colon will be inspected using the forward-facing view (standard of care). The colonoscope will then be re-advanced to the cecum and again withdrawn using the forward-facing view.

During colonoscopy, any polyps that are found will be removed and any cancers noted will be biopsied (standard of care). 300 patients will be recruited at each site (Stanford and MGH), and the number of precancerous lesions (polyps) and cancers found at colonoscopy utilizing the two different colonoscopes will be evaluated. The adenoma detection rate (ADR), the adenoma per colonoscopy (APC) rate and the adenoma miss rate (AMR) at first pass for the two colonoscopes will be calculated.

The major endpoints are number of precancerous or cancerous lesions found during colonoscopy. We do not plan to terminate the study before enrollment has been met. The study will be terminated at the enrollment of 300 participants at each of the two sites.

6. Data sources will include procedure report, patient's electronic medical record, pathology reports and demographic information. These will be recorded in a confidential manner with PHI de-identified.

Inclusion Criteria:

1. Ability to provide informed consent
2. Adult men and women age 40 years old or older
3. Colonoscopy patients with a history of adenomatous colorectal polyps and are returning for a follow up colonoscopy 3 yrs or more after their previous procedure

Exclusion Criteria:

1. Poor or fair bowel preparation
2. Difficult first insertion of colonoscope
3. Conserved status
4. Familial polyposis
5. Inflammatory bowel disease
6. Pregnancy
7. Active GI bleeding
8. Prior colonic or rectal resection (colon not intact)
9. Screening colonoscopy
10. Colonoscopy done to evaluate symptoms like abdominal pain, diarrhea, constipation, change in bowel habit.

VI. BIostatistical Analysis

The primary endpoint is the adenoma detection rate (ADR) for the control and Retroview group. The ADR is the percentage of patients with at least one adenoma. The numbers will be compared using standard statistical analysis of proportions (e.g., <http://www.ltconline.net/greenl/courses/201/estimation/ciprop.htm>). Both groups will be assumed to be normally distributed. Secondary endpoints will be the ADR for each pass of the colonoscope (i.e., the incremental adenoma pick-up rate), the overall polyp detection rate (adenomas and non-adenomas) and the mean number of adenomas identified per patient with polyps. We hypothesize that the Retroview colonoscope will detect additional adenomas at a rate of 30% compared to the a rate of 20% when using a

conventional colonoscope. Assuming a significance level of 5% and a power level of 80%, 294 patients in each arm (total of 588 patients) would be required to demonstrate this improved performance.

VII. RISKS AND DISCOMFORTS

The risk of perforation of the colon during screening/surveillance colonoscopy with polypectomy is 1:1000. There is risk of bleeding following polypectomy, but bleeding is readily fixable. These risks would apply to the patients regardless of whether they choose to participate in the study or not. It is not anticipated that participation in this study will directly pose any psychological risks to the patient.

VIII. POTENTIAL BENEFITS

The potential benefits to study subjects will be an improved colonoscopy with fewer missed precancerous (polyps) and cancerous lesions. In addition, both arms of the study will benefit by a more thorough examination of the colon (second look colonoscopy), as data from numerous studies confirms that a second look increases the number of precancerous polyps that are detected at colonoscopy. Identification of an improved colonoscope may aid future patients who undergo screening and surveillance colonoscopy in order to prevent colorectal cancer.

IX. MONITORING AND QUALITY ASSURANCE

This study will be closely monitored by [name], Director of Quality Assurance for the MGH GI Unit and [name], the Principal Investigator of this study. [name] oversees Quality Assurance for all gastrointestinal endoscopic procedures and [name] as the Principal Investigator of this trial, will be responsible for ensuring that the study is conducted according to the IRB-approved protocol and regulations, and for protecting the rights, safety and welfare of the subjects. [name] or another physician investigator will be responsible for obtaining informed consent from study participants. [name] will be responsible for reporting any adverse events to the IRB. In accordance with Partners Human Research Committee (PHRC) guidelines, adverse events will be reported to the PHRC along with appropriate forms within the required time frame. [name] is the principal investigator of this study and is directly responsible for the conduct of the study.

This is a two site study. When 100 subjects have been enrolled at a site, de-identified study data will be jointly reviewed by the lead investigators at the two sites. Any serious adverse event will be reviewed by the two lead investigators within 48 hours. The two lead investigators will be responsible for determining whether the research should be altered or stopped.

X. REFERENCES

Embedded within the body of this document.

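### Two exclusions can take effect only after randomisation, and the plan has no analysis set, replacement rule or loss allowance to protect the sample size or the ADR comparison

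*Combined protocol and SAP*

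**What the plan says.** The numbered steps of Section V run in this order: bowel preparation, an approach at the pre-procedure examination, consent and randomisation, then colonoscopy. On randomisation the text is: "Following consent, patients will be randomized to colonoscopy with either the new colonoscope or conventional colonoscope".

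The exclusion criteria at the end of Section V open with "Poor or fair bowel preparation". The second is a difficult first insertion of the colonoscope. The plan does not say when either is assessed, or what happens to a patient who meets one after randomisation.

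On numbers, Section V says: "The study will be terminated at the enrollment of 300 participants at each of the two sites". Section VI says: "294 patients in each arm (total of 588 patients) would be required to demonstrate this improved performance". Section IV, by contrast, gives 300 as the total enrolment for the study.

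The plan does not define enrolment and does not describe an analysis set. It has no replacement rule, and it makes no allowance for loss in the sample size.

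**The concern.** An exclusion that operates after randomisation differs from an entry criterion in two ways.

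First, it uses up sample. If enrolment is counted at consent or randomisation and excluded patients are left out of the comparison, the number analysed is smaller than the number at which recruitment stops. Section VI sizes the trial with almost nothing to spare.

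Second, it can break the comparability that randomisation gives. Both criteria are judgements, and the documents describe no blinding of the endoscopist, who has the assigned scope in hand. The two criteria are not equally exposed. Bowel preparation is completed before randomisation, so its true quality cannot depend on the arm; only its rating can. Ease of insertion can depend on the instrument itself, so an exclusion on that ground may remove different kinds of patient from the two arms. What is at stake is the primary ADR comparison, in both its power and its validity.

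**Working it through.** **Inputs.** From Section VI: rates of 30% and 20%, significance level 5%, power 80%, 294 per arm. From Section IV: equal allocation. From Section V: 300 enrolled at each of two sites, 600 in all. Sidedness is not stated; two-sided is inferred because a one-sided 5% test would need only 231 per arm.

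**Reproducing the plan's figure.** For the normal test of two proportions with pooled null variance (mean rate 0.25):

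n per arm = [1.960·√(2·0.25·0.75) + 0.842·√(0.20·0.80 + 0.30·0.70)]² / 0.10²

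= [1.2002 + 0.5119]² / 0.01 = 293.2, rounded up to 294.

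This matches the plan. The 588 is therefore the bare formula result, with nothing added for loss.

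**Margin.** 600 − 588 = 12, and 12/600 = 2.0%.

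**Power after loss.** With a proportion x lost equally from both arms, n = 300(1 − x) and

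power = Φ{(0.10·√n − 1.2002) / 0.6083}

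where 0.6083 = √0.37. For example, at x = 10%, n = 270, √n = 16.432, and (1.6432 − 1.2002)/0.6083 = 0.728, which gives 76.7%.

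| Assumed loss | Analysed | Power | Total to randomise to keep 588, i.e. 588/(1 − x) |
|---|---|---|---|
| 0% | 600 | 80.9% | 588 |
| 2% | 588 | 80.1% | 600 |
| 5% | 570 | 78.9% | 619 |
| 10% | 540 | 76.7% | 654 |
| 15% | 510 | 74.3% | 692 |
| 20% | 480 | 71.7% | 735 |
| 25% | 450 | 68.9% | 784 |

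The documents give no rate of exclusion at the procedure, so the first column is an assumed range.

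**Sensitivity to the formula.** With unpooled variance the requirement is 290.4, so 291 per arm (582 in total), and the margin becomes 18/600 = 3.0%. With a continuity correction it is 313 per arm (626 in total), so 600 is already short, with power of 78.2%.

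**The other enrolment figure.** If Section IV's 300 were the true total, n would be 150 per arm and power 51.6% before any loss. Only 300 per site is consistent with 588.

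**Bias.** Its size cannot be calculated. The documents give neither the frequency of either exclusion by arm nor the ADR among those who would be excluded.

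**The case against.** The strongest reply is that the shortfall depends on a word the plan never defines. Someone who meets an exclusion might not count as enrolled, in which case 300 per site means 300 eligible patients and no numbers are lost. Nor does the plan say that excluded patients leave the comparison. This stands: the loss is conditional. A reader might infer that the plan, followed as written, necessarily uses up its own sample; the text does not go that far. What remains is that the counting and analysis rule is missing where it decides the result. Counting only eligible patients would restore the number but not remove the possible bias, since selection would still follow randomisation.

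It can also be said that the plan does not state when preparation is rated, and that some poor preparation might be noticed before randomisation. That is fair; the timing is an inference. Difficult first insertion needs no such inference.

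A reader might further infer that a loss above 2% is likely because fair as well as poor preparation is excluded, or that power collapses beyond 2%. The documents support neither. They give no rate, and power declines gradually: at 5% loss it is about one point below target.

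On bias, Section I cites a study in which a prototype with a short bending section reached the cecum as well as a standard one. That makes a large difference in insertion less likely, but it concerned a prototype and reaching the cecum, not an operator's judgement of difficulty with this scope.

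Finally, Section VI attaches 30% and 20% to the detection of additional adenomas, whereas ADR is the percentage of patients with at least one. The power figures above take the plan's rates as it uses them and do not validate them for ADR.

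**Conclusion.** The concern holds in conditional form. At least one exclusion, and probably two, takes effect after randomisation, and the plan does not say how those patients are counted, replaced or analysed. If they count toward 300 per site and are dropped from the analysis, the allowance is 12 patients (2.0%, or 3.0% with unpooled variance). Power would then be about 1 point below the 80% target at 5% loss, 3 points at 10% and 8 points at 20%. These figures rest on the plan's 30% versus 20%, a two-sided test, equal loss in the arms, and loss rates that are assumptions.

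The power loss alone is modest at low rates and would not show the trial to be inadequate. The possible bias is the stronger reason to act: selection after randomisation, on a judgement made with the assigned scope in hand, puts the primary comparison at risk whatever the final count. The documents do not show that such bias will occur, or in which direction.

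**What to change.** 1. In Section VI, define the primary ADR comparison as including all randomised patients who undergo colonoscopy, each in the arm assigned.
2. In Section V, record preparation quality and insertion difficulty for every patient. In Section VI, report the comparison restricted to good or excellent preparation and non-difficult insertion as a sensitivity analysis.
3. If the sponsor prefers to keep the two exclusions in the primary analysis, say when each is assessed and whether such patients count toward 300 per site. Restate the power in Section VI for the number expected to be analysed, over a stated range of loss such as 5% to 20%.
4. Reconcile the total of 300 in Section IV with 300 per site in Section V.

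The cost is wording and two recorded items, with no extra patients or procedures. Under items 1 and 2, some less well-prepared colons and difficult procedures stay in the main analysis and may dilute the difference slightly, so 80.9% at 600 assumes that 30% versus 20% still holds with them included. Under item 3, the stated power falls below 80% once loss exceeds about 2%, and the possible bias remains.

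### Section VI does not tie its 80% power to the primary endpoint: 20% and 30% are given for additional adenomas, and no expected ADR is stated

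*Combined protocol and SAP*

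**What the plan says.** All references are to the combined protocol and SAP.

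- Section VI, primary endpoint: "The primary endpoint is the adenoma detection rate (ADR) for the control and Retroview group". It is defined per patient: "The ADR is the percentage of patients with at least one adenoma". The arms are to be compared as proportions.
- Section VI, secondary endpoints: "Secondary endpoints will be the ADR for each pass of the colonoscope (i.e., the incremental adenoma pick-up rate", among others.
- Section VI, sizing: "We hypothesize that the Retroview colonoscope will detect additional adenomas at a rate of 30% compared to the a rate of 20"% with a conventional colonoscope. At 5% significance and 80% power, "294 patients in each arm (total of 588 patients) would be required to demonstrate this improved performance".
- Sections IV and V: patients in both arms have two withdrawals. The second is retroflexed with the new colonoscope and forward-viewing in the control arm.
- Section I, on retrograde-viewing devices, reports an earlier tandem study: "The second look by Third Eye colonoscope found more additional adenomas (46% more) than a second look by standard colonoscope (20% more").
- Section IV, enrolment: "A total of 300 subjects will be enrolled", with equal randomisation. Section V: "The study will be terminated at the enrollment of 300 participants at each of the two sites".

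No section gives an expected ADR for either arm. Section V also describes the major endpoints as lesion counts, which differs from the patient-level primary in Section VI.

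**The concern.** The power statement should refer to the quantity that the primary analysis tests. Here the tested quantity is whole-procedure ADR, while the assumed rates concern additional adenomas, with no numerator, denominator or pass. With two passes in each arm, additional most naturally means beyond the first pass. That matches the secondary per-pass measure and the way Section I uses the term for second-look findings.

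The distinction matters because an extra adenoma in a patient who already had one on the first pass leaves ADR unchanged. If 20% and 30% are second-pass yields, the new colonoscope could perform exactly as hypothesised while the ADR comparison had much less than 80% power. A null primary result would then be hard to interpret.

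**Working it through.** **Inputs from the documents.** 20% and 30%, 5% significance, 80% power, 294 per arm, 1:1 allocation, a comparison of proportions (Section VI; allocation from Section IV). Sidedness is not stated; two-sided is assumed because it reproduces the plan's figure.

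**Inputs assumed here.** The first-pass ADR f, taken as equal in both arms, and the overlap between passes. Neither is in the documents, so ranges are shown.

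**Formulas.** With p̄ = (p1 + p2)/2, d = p2 − p1 and V = p1(1−p1) + p2(1−p2):

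- n per arm = [1.960·√(2p̄(1−p̄)) + 0.842·√V]² / d²
- power = Φ{[d·√n − 1.960·√(2p̄(1−p̄))] / √V}, plus the small opposite tail

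**Step 1: reproduce the plan's figure.** For 0.20 vs 0.30, p̄ = 0.25. Then 1.960·√0.375 = 1.2002 and 0.842·√0.37 = 0.5119. (1.2002 + 0.5119)² / 0.01 = 293.2, so 294 per arm. Power at 294 is Φ[(1.7146 − 1.2002)/0.6083] = Φ(0.846) = 80.1%. The arithmetic in Section VI is correct.

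**Step 2: 20% and 30% are whole-procedure ADRs.** Power for the primary is 80% at 294 per arm.

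**Step 3: they are second-pass patient yields, independent of the first pass.** ADR = f + (1−f)·0.20 vs f + (1−f)·0.30. The same expressions hold if the yields apply only to patients negative on pass 1. For f = 0.40 the ADRs are 0.52 and 0.58, and power at 294 is Φ[(1.0288 − 1.3790)/0.7023] = Φ(−0.499) = 31%.

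| Assumed first-pass ADR | ADR, control vs Retroview | Power at 294 per arm | n per arm for 80% |
|---|---|---|---|
| 20% | 36% vs 44% | 51% | 588 |
| 30% | 44% vs 51% | 40% | 798 |
| 40% | 52% vs 58% | 31% | 1079 |
| 50% | 60% vs 65% | 24% | 1471 |
| 60% | 68% vs 72% | 18% | 2060 |

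(The 588 in the first row is per arm; that it equals the plan's total is a coincidence.)

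**Step 4: the same yields, with the passes dependent.** Let s be the share of patients with a second-pass adenoma who had none on pass 1. ADR = f + 0.20s vs f + 0.30s; independence is s = 1 − f.

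| f | s | ADR, control vs Retroview | Power at 294 per arm |
|---|---|---|---|
| 40% | 0.5 | 50% vs 55% | 23% |
| 40% | 0.6 (independence) | 52% vs 58% | 31% |
| 40% | 0.75 | 55% vs 62.5% | 46% |
| 40% | 1 | 60% vs 70% | 72% |
| 50% | 1 | 70% vs 80% | 80% |
| 60% | 0.9 | 78% vs 87% | 82% |
| 60% | 1 | 80% vs 90% | 93% |

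Within first-pass ADRs of 20% to 60%, power reaches 80% only when f is about 50% or more and nearly all second-pass patients had no first-pass adenoma.

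**Step 5: a 10-point ADR gap at other control ADRs.** Power at 294 per arm is 86% at a control ADR of 15%, 80% at 20%, 72% at 30%, 68% at 40% to 50%, 72% at 60%, 80% at 70%, 86% at 75% and 93% at 80%.

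**Step 6: enrolment, a separate matter.** Section IV: 300/2 = 150 per arm. Section V: 2 × 300 = 600, so about 300 per arm. Section VI: 588/2 = 294 per arm. For 20% vs 30%, power is 81% at 300 per arm. At 150 it is Φ[(1.2247 − 1.2002)/0.6083] = Φ(0.040) = 52%.

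**The case against.** The best defence is that the rates are loosely worded ADRs. One paragraph names ADR, defines it per patient, says it will be compared as proportions and then gives 20%, 30% and a sample size. The two-proportion formula returns exactly 294. This reading remains open, and if it is right the defect is one phrase. But the match shows only that two proportions were entered, not which two: second-pass patient yields of 20% and 30% give the same 294.

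A second objection is that low power is not inevitable even if the rates are not ADRs. That stands. Participants have prior adenomas and two passes, and nothing in the documents rules out a control ADR of 70% or more, where a 10-point gap has at least 80% power.

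Two stronger readings are tempting. A reader might infer that the trial is underpowered for its primary endpoint. The documents do not support this, because they give no ADR from which to calculate it. A reader might also infer that 20% and 30% are increases in lesion counts, given the Section I figures and the lesion-count endpoints in Section V. But Section VI calls the per-pass measure an ADR, and the retrograde figure in Section I is 46%, not 30%. A power figure on that reading would need a mean and dispersion that the documents lack, so none is offered.

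Finally, the 150-per-arm case rests on one sentence in Section IV. Section V states 300 per site more than once, and 600 accommodates 588. It is fair to treat this as a separate contradiction rather than as part of the size of the endpoint problem.

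**Conclusion.** The point holds in a limited form and should be fixed before the power statement is relied on. The 294 is correctly calculated, but 80% power for the primary is not established, because the rates behind it are undefined and no expected ADR is given. Confidence is high on that statement. It does not extend to saying which rates were meant or that the trial is underpowered.

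The size of the gap depends on the reading: none if the rates are whole-procedure ADRs, and large under independent second-pass yields. The second-pass figures rest on assumed first-pass ADRs, equal in the two arms, and on the assumed overlap between passes. The enrolment contradiction needs no such assumption: the Section IV total cannot supply the 588 that Section VI requires.

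**What to change.** 1. In Section VI, state the unit (patients or lesions) and the pass to which 20% and 30% apply, and the assumed whole-procedure ADR in each arm.
2. If those ADRs are 20% and 30%, say so and keep 80% for the primary. If not, restate the ADR power at the planned size. In that case, attribute 80% to the second-pass endpoint, defined as the proportion of patients with at least one additional adenoma on pass 2 and assumed to be 20% vs 30%.
3. Reconcile Section IV with Sections V and VI to one enrolment figure, and quote power at that figure.
4. Reconcile the lesion-count endpoints in Section V with the ADR primary in Section VI.

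**Cost.** The edits are to text and need no new trial data. The sponsor must supply an assumed ADR per arm, which the documents lack. The downside is that the stated power for the primary may become less favourable. The sponsor would then have to accept that figure openly or consider a design change, such as re-sizing or aligning the primary endpoint with the powered quantity.
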